#### **13.4. Secondary Endpoints**

The Kaplan-Meier method will be used to estimate overall survival and progression-free survival distributions. Each of these variables will be measured from the start date of the treatment to the date of the event (i.e., death or disease progression) or the date of last follow-up to evaluate that event. Similarly, we will also evaluate duration of objective response in the subset of patients who achieve a response to treatment, where we will define this from the date of documentation of response to the date of progression and/or death. This will be more exploratory and descriptive given the expected response rate, but we will use the methods of Kaplan and Meier to evaluate this. Overall survival will only be evaluated for Part 2, where for Part 1 patients who progress and go on to Part 2 will be censored at that time making the estimation not as informative. Progression-free survival will not be confounded due to the fact that Part 1 patients need to progress first before going to the Part 2 treatment regimen. The clinical benefit rate (CR+PR+SD) will be reported for patients after Part 1 and after Part 2.

**Toxicity and tolerability:** As per NCI CTCAE v4.0, the term toxicity is defined as adverse events that are classified as either possibly, probably, or definitely related to study treatment. The maximum grade for each type of toxicity will be recorded for each patient, and frequency tables will be reviewed to determine toxicity patterns. In addition, we will review all adverse event data that is graded as 3, 4, or 5 and classified as either “unrelated” or “unlikely to be related” to study treatment in the event of an actual relationship developing. The incidence of severe (grade 3+) adverse events or toxicities will be described. We will also assess tolerability of the regimens for part 1 and part 2 through assessing the number of patients who required dose modifications and/or dose delays. In addition, we will also capture the proportion of patients who go off treatment due to adverse reactions or even those who refuse further treatment for lesser toxicities that inhibit their willingness to continue participation on the trial. These tolerability measures will be assessed within each of the treatment parts independently. All patients who have received at least one dose of any of the therapeutic agents will be evaluable for toxicity and tolerability.

**Correlative endpoints:**

The statistical analysis corresponding to the correlative studies will be descriptive and exploratory in nature.

**RPPA:**

For each patient the protein intensity fold-change ratios will be calculated from the RPPA intensity values. Ratios between tumors sampled prior to initiating trametinib single agent treatment and at time of progression on either single agent trametinib or the combination (TOP/pre-treat ratio), will be calculated. These ratios will be median-centered and clustered using Cluster 2.0 software (<http://rana.lbl.gov/EisenSoftware.htm>). Student’s t-test for differences between average protein intensity ratios at these intervals will be calculated using Microsoft Excel by grouping all the ratios for individual clusters.

Table 4	Biomarker Prevalence				
	10%	20%	30%	40%	50%

HR	0.43	0.51	0.55	0.56	0.57
----	------	------	------	------	------

These results and exploratory analyses will be used in planning future studies of this

combination treatment regimen in this patient population. Biomarker analyses on required research biopsies at study entry will be conducted to assess the predictive value of PTEN and other biomarkers on patient outcome. For example, we will assess impact of PTEN status and other markers on survival outcomes as well as ORR and CBR. For survival-based outcomes, Table 4 shows detectable hazard ratios between marker groups for varying prevalence rates and at least 80% power. The Type I error constraint is quite lax in this setting, reflecting a phase II approach and relaxation of constraints but also in the univariate setting can be used to cast a wider net to capture potential markers of interest that may provide insights for the development of future biomarker-driven therapeutic strategies. Fisher exact tests will also be used to identify potential differences in ORR and CBR rates between biomarker groups as well, although depending on prevalence rates we will likely have sufficient power to only detect large differences (e.g. 35%) if we constrain Type I error to 0.05. Again, these will be largely exploratory, and lack of significant results will be viewed with caution given these limitations but will provide

**Table 1: Statistical Considerations for Biomarker Analysis.** Maximum detectable hazard ratios (HR) using one-sided log-rank test with 80% power and alpha=0.2, assuming a sample size of 37, 26 months accrual and 12 months follow-up.

insights into potential relationships and mechanisms. To assess mechanisms of acquired resistance, research biopsies will be conducted at time of progression on trametinib monotherapy and at time of progression to the combination of trametinib and GSK2141795. Restaging will

occur after every 2 treatment cycles (8 weeks).

Whole exome and transcriptome sequencing:

Genetic alterations from whole exome sequencing data would be tabulated. Data analysis will be conducted in collaboration with computational biologists in the [name] lab / Broad Cancer Program computational group. Whole exome sequencing data will be analyzed for base substitutions, small insertions and deletions, copy number alterations, and loss of heterozygosity. Selected alterations of interest will be validated by Sanger sequencing or related orthogonal technologies in use in the [name] lab. Data will be compiled to generate a catalogue of candidate genomic alterations that cause resistance to MEK and ATK inhibition. Genes listed above in Section 9, Table 3 will be the first to be examined as well-known genes related to cancer growth and survival. Molecular alterations of known significance will be reported. Molecular alterations of unknown significance will also be presented; however, assessment of the clinical significance will be investigated by *in vitro* studies (i.e. site-directed mutagenesis, growth inhibition analysis, immunoblot studies, and kinase assays).. Identified markers of interest will be explored in relation to several clinical outcomes of interest for each treatment component. Specifically, we will look at incidence of mutations and marker expression levels similar to that described above, where we will first look graphically at associations with objective response as well as with progression-free survival. Model-based evaluations may also be used in an exploratory manner to better assess these relationships in a quantitative manner, but will be limited given the sample size available for these analyses.

QTAP/Kinome assay:

D=Difference in log 2 scale	1.00	1.58	2.00	2.32
Fold change (2 D )	2	3	4	5
Power (%)	8.93	81.69	97.39	99.61

Table 5 summarizes the power to detect a true difference of D with a sample size of 9 patients in each group (pre and post treatment)

For the QTAP/Kinome assay: Paragon Algorithm software will be used to quantify changes in bound kinase levels. As seen in Table 5, a two-sided paired sample t-test will have at least 80% power to detect a 3-fold change in bound kinase levels before and after treatment with 9 patients in each group (assuming Type I error of 0.05). Based on preliminary data, we assume that 100 kinases are captured, of which 10% of them are truly differentially expressed between pre- and post- treatment and a common standard deviation of 0.95 (in log2 scale, Table 5). Given the limited paired sample size, nonparametric tests will be used (i.e. Wilcoxon signed rank test) if approximate normality is not achievable through transformation.

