### 2.3. Rationale

Triple negative breast cancer (TNBC) is often characterized by high expression of epidermal growth factor receptor (EGFR). Hoeflich *et al.* demonstrated that activation of EGFR leads to cell signaling along the RAF/MEK/ERK pathway, and subsequent treatment with a MEK-targeted drug caused reduced tumor growth in basal-like breast cancer models. One proposed mechanism of intrinsic resistance to MEK inhibition is through the ERK-independent PI3K/AKT pathway, as basal-like breast cancer cell lines with loss of PTEN (an inhibitor of the PI3K pathway) or high levels of AKT signaling were less responsive to MEK inhibition. This preclinical finding may be clinically relevant as 30% of women with basal-like breast cancer demonstrate evidence of PTEN loss. Additionally, treatment with a selective MEK inhibitor resulted in upregulation of the PI3K/AKT pathway.

To validate these findings, [name] (Chair of Cancer Research and Therapy at the Ohio State University, scientific collaborator) performed a series of preclinical *in vitro* experiments. Basal-like breast cancer cell lines were treated with trametinib monotherapy (Unpublished data [name], [name]). As predicted, treatment of basal-like breast cancer cell lines

with trametinib was associated with greater cell kill in the PTEN wild type MDA-MB-231 cell line compared to PTEN null MDA-MD-468 (Figure 2). Our results are consistent with the findings of Hoeflich *et al.* suggesting that MEK inhibition depends in part on PTEN status.

[figure not shown]

Figure 2. Trametinib (GSK1120212) monotherapy in basal-like breast cancer cells MDA-MD468 (PTEN null) and MDA-MB-231 (PTEN wild type) (Unpublished data, [name] and [name]).

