## 9. BIOMARKER, CORRELATIVE, AND SPECIAL STUDIES

### 9.1. Collection of Specimen(s)

The primary hypothesis of the correlative component to this trial is that biomarkers of sensitivity and resistance to MEK inhibition can occur through ERK-dependent and ERK-independent pathways. To test this hypothesis we propose correlative studies on research biopsies acquired at these time points 1) in all patients prior to trametinib monotherapy (mandatory) 2) all patients after progression on Part 1 with trametinib (mandatory) 3) all patients at time of progression on trametinib combined with GSK2141795 (optional). In addition, archival FFPE sections, plasma and a whole blood samples will be collected..

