### Study Calendar

Study Assessment s 	Screen	Part 1 Trametinib monotherapy	Part 2 Trametinib in combination with GSK2141795	Final Study Visit 	Post Treatment Follow Up 
Informed Consent	X				
Baseline Demographics	X				
Medical History / Interim History	X	Day 1 ( $\pm 3$ days) of each cycle	Day 1 ( $\pm 3$ days) of each cycle	X	
Concomitant Medications	X	Continuous			
Physical Exam	X	Day 1 ( $\pm 3$ days) of each cycle	Day 1 ( $\pm 3$ days) of each cycle	X	
ECOG Performance Status	X	Day 1 ( $\pm 3$ days) of each cycle	Day 1 ( $\pm 3$ days) of each cycle	X	
Vital Signs (BP, HR, Temperature, weight)	X	Day 1 ( $\pm 3$ days) of each cycle	Day 1 ( $\pm 3$ days) of each cycle	X	
Hematology, Clinical Chemistry 	X	Day 1 ( $\pm 3$ days) of each cycle	Day 1 ( $\pm 3$ days) of each cycle	X	
Pregnancy Test 	X				
Hemoglobin A1C, TSH, fasting glucose	X	Repeated every 3 cycles $\pm 7$ days or as Clinically Indicated			
Fingerstick blood glucose			At home daily monitoring for weeks 1 -4, then as clinically indicated	As Clinically Indicated	
12-Lead ECG	X		Prior to dosing on Week 1 day 1 and day 15, and then every 4 weeks (Week 5, Week 9, etc.) $\pm 7$ days or as clinically indicated		

Study Assessments 	Screen	Part 1 Trametinib monotherapy	Part 2 Trametinib in combination with GSK2141795	Final Study Visit 	Post Treatment Follow Up 
LVEF (ECHO)	X	Repeated every 3 cycles $\pm$ 7 days during Part 1 or as Clinically Indicated	Week 5, Day 1 of Part 2 and then at the start of every 12 weeks $\pm$ 7 days or as clinically indicated	As Clinically Indicated	
Ophthalmic Exam 	X	As Clinically Indicated			
Blood sample 		Day 1 ( $\pm$ 3 days) of cycle 1			
Plasma 	X	Day 1 cycle 2 and at progression	Day 1 of cycle 2 (prior to dosing)	X	
Research Biopsy(s) 	Mandatory research biopsies will be attempted on all patients prior to the initiation of study treatment on Part 1	Mandatory research biopsies will be attempted on all patients at time of progression on Part 1	Optional research biopsies will be attempted on patients at time of progression on Part 2		
Study Agents		Trametinib will be administered daily in Part 1. Trametinib will be administered in combination with GSK2141795 in Part 2. Please see Section 6 for Dose Modifications.			

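### The only RPPA change measure for progression on the combination starts from pre-trametinib tissue, so it cannot separate change arising on the combination from change already present at Part 1 progression

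*Combined protocol and SAP*

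**What the plan says.** Section 13.4, under RPPA, computes "Ratios between tumors sampled prior to initiating trametinib single agent treatment and at time of progression on either single agent trametinib or the combination" and names the result the TOP/pre-treat ratio. The denominator is the same whichever regimen the patient progressed on. After median-centering and clustering comes a t-test, described in these terms: "differences between average protein intensity ratios at these intervals will be calculated using Microsoft Excel by grouping all the ratios for individual clusters".

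The same section states: "Biomarker analyses on required research biopsies at study entry will be conducted to assess the predictive value of PTEN and other biomarkers on patient outcome". No other tissue is named for prediction.

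The Study Calendar provides a sample between the two parts: "Mandatory research biopsies will be attempted on all patients at time of progression on Part 1". Section 9.1 also makes that biopsy mandatory, and makes the biopsy at progression on the combination optional. Nowhere do the documents divide combination-progression tissue by Part 1 progression tissue, or name the Part 1 progression biopsy as the baseline for Part 2.

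Section 1.2 asks for molecular markers of sensitivity and resistance both to trametinib alone and to the combination. Section 13.4 describes all correlative analyses as descriptive and exploratory.

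**The concern.** Most patients reach the combination after progressing on trametinib, so their tumors have already been altered by Part 1. The Rationale (2.3) expects this: "treatment with a selective MEK inhibitor resulted in upregulation of the PI3K/AKT pathway". Part 2 asks whether adding an AKT inhibitor overcomes that resistance.

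A ratio that reaches back past Part 1 misleads in two ways. A protein that rose on trametinib and did not move on the combination still shows a change at combination progression. A protein that rose on trametinib and was brought back down on the combination shows none. The second pattern is the one the Part 2 hypothesis would most want to see.

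A related but different gap concerns prediction. Entry tissue cannot show resistance acquired during Part 1, and section 13.1 names acquired resistance as something the combination should overcome.

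**Working it through.** **Notation.** PRE is the biopsy before trametinib, TOP1 the biopsy at progression on trametinib, and TOP2 the biopsy at progression on the combination.

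**Identity.** TOP2/PRE = (TOP1/PRE) × (TOP2/TOP1), so log(TOP2/PRE) = log(TOP1/PRE) + log(TOP2/TOP1).
- 3-fold rise in Part 1, no change in Part 2: 3 × 1 = 3.
- 3-fold rise in Part 1, full return in Part 2: 3 × 1/3 = 1.

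**Does the planned t-test repair this?** Paired within patient on the log scale, log(TOP2/PRE) − log(TOP1/PRE) = log(TOP2/TOP1), and the shared denominator cancels. On raw ratios it does not. Take two patients with the same 2-fold Part 2 change. If TOP1/PRE = 2, then TOP2/PRE = 4 and the difference is 2. If TOP1/PRE = 0.5, then TOP2/PRE = 1 and the difference is 0.5. The plan states neither pairing nor a log scale, and it groups ratios by cluster.

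**Inputs for a size.** The plan gives no SD or number of pairs for RPPA. The only paired before/after figures are those for the kinome assay (13.4 and Table 5): 9 pairs, SD 0.95 on the log2 scale, two-sided test, Type I error 0.05, and 100 kinases of which 10% truly change.

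**Reproducing Table 5.** The power is that of a paired t-test with 8 df and noncentrality (D/0.95) × √9. This is 3.16 at D = 1.00 (2-fold) and 4.99 at D = 1.58 (3-fold). Read as a 5% false discovery rate, the 0.05 gives a per-test level α* = (10 × power × 0.05)/(90 × 0.95), solved together with the power:
- D = 1.00: α* = 0.04465/85.5 = 0.00052, power 8.93%.
- D = 1.58: α* = 0.40845/85.5 = 0.0048, power 81.69%.
- D = 2.00 and 2.32: power 97.39% and 99.61%.

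All four match Table 5. A plain per-test 5% level does not: it gives 78.95% at D = 1.00 and 99.1% at D = 1.58.

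**Applying this to TOP2/PRE with no combination effect.** The tested contrast then carries the Part 1 shift in full, so the chance of flagging a change is the power at that shift.

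| Part 1 change carried through | 5% FDR, 9 pairs | Unadjusted 5%, 9 pairs | Unadjusted 5%, 5 pairs |
|---|---|---|---|
| 2-fold | 8.93% | 79% | 44% |
| 3-fold | 81.69% | 99% | 79% |

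In 40,000 simulated trials of 9 patients at the unadjusted level, TOP2/TOP1 was flagged about 5% of the time whatever the Part 1 shift. An unpaired comparison of the two log ratios was flagged about 1% of the time. With equal independent noise the two ratios share variance s² out of 2s² each, a correlation of 0.5 that an unpaired test ignores. The unpaired version is therefore conservative.

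**The case against.** The strongest answer is that the t-test at these intervals may be meant to compare the combination ratio with the monotherapy ratio, which would recover the Part 2 increment. That reading is natural, and nothing rules it out. It works only with pairing and logs, which the plan leaves unstated, so the need to specify the contrast stands.

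Other objections limit the point:
- A reader might infer that the plan counts Part 1 changes as combination effects. It does not say so: the ratio is never labelled a combination effect. The defect is that it cannot separate the two.
- A reader might extend the defect to the predictor analysis. That does not follow. Entry tissue misses Part 1 change; it does not attribute it to the combination. The PTEN objective concerns single-agent trametinib, for which entry tissue is right. Section 2.3 expects better response with MAPK/PI3K co-activation but does not say when it must be measured.
- A reader might quote 79% for a 2-fold change as the plan's own figure. Under the criterion that reproduces Table 5 it is about 9%.
- Sequencing is a weak target. Section 9.2.2 includes matched normal DNA from blood, and its sample sets do not exclude the Part 1 progression biopsy.
- Under 13.3, if Part 1 stops early, later patients may receive the combination directly. For them pre-treatment tissue is the correct baseline.
- The analyses are exploratory, and TOP2/TOP1 could still be computed wherever both samples exist.

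**Conclusion.** The point holds for the RPPA ratio, and for any kinome pairs taken at combination progression if they too use pre-trametinib tissue as baseline. The stated measure mixes Part 1 and Part 2 change by construction, and the text does not secure the one analysis that would separate them. This follows from algebra and rests on no numerical assumption.

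The size is illustrative only. It borrows the kinome SD and number of pairs, assumes no true combination effect, and uses log ratios before any median-centering. It is sensitive to error control at 2-fold (about 9% against 79%) but high at 3-fold either way (82% or 99%). Combination-progression biopsies are optional, so there may be fewer than 9 pairs. No error in Table 5 is implied, and no efficacy conclusion or ORR decision rule depends on this.

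**What to change.** In 13.4, define on the log scale and paired within patient:
- **Part 1 change:** trametinib-progression biopsy over pre-trametinib biopsy.
- **Part 2 change:** combination-progression biopsy over trametinib-progression biopsy.
- **Cumulative change:** combination-progression biopsy over pre-trametinib biopsy, kept and labelled as such.

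Use the same Part 2 baseline for any kinome pairs taken at combination progression. State that patients who receive the combination without Part 1 keep the pre-treatment biopsy as baseline.

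For Part 2 outcomes, add an exploratory marker analysis on the Part 1 progression biopsy where available. It should stand alongside the study-entry analysis, not replace it.

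The cost is analysis wording, with no new procedure. Patients without a usable Part 1 progression biopsy drop out of the Part 2 ratio. That loss may not be trivial: biopsies are only attempted, and section 9.4.2 accepts less than the target amount of tissue. The number of patients contributing to each ratio should be reported.

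### The RPPA plan averages, clusters and t-tests fold-change ratios with no stated log step, which overstates average increases and mainly costs power

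*Combined protocol and SAP*

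**What the plan says.** The RPPA paragraph of Section 13.4 sets out four steps.

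- **Variable.** "For each patient the protein intensity fold-change ratios will be calculated from the RPPA intensity values". Each ratio divides the value at progression, on trametinib alone or on the combination, by the value before treatment: "time of progression on either single agent trametinib or the combination (TOP/pre-treat ratio), will be calculated".
- **Pre-processing.** "These ratios will be median-centered and clustered using Cluster 2.0 software".
- **Test.** A Student's "t-test for differences between average protein intensity ratios at these intervals will be calculated using Microsoft Excel".
- **Unit.** The test is done "by grouping all the ratios for individual clusters".

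No log step, normality check or nonparametric alternative is given for RPPA. Pairing, sidedness and alpha are not stated either. Section 9.2.1.2 describes loading normalization and curve-fitted concentrations, and does not give the output scale.

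The QTAP/Kinome part of Section 13.4 handles the same kind of change differently. Table 5 is in log2, the power rests on "a common standard deviation of 0.95" in log2 units, and a signed rank test is the fallback if transformation does not give approximate normality.

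All of this comes under the statement "The statistical analysis corresponding to the correlative studies will be descriptive and exploratory in nature".

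**The concern.** A ratio is not symmetric about no change. A doubling (2.0) and a halving (0.5) are equal and opposite, yet their average is (2.0 + 0.5)/2 = 1.25. In log2 they are +1 and -1 and average to 0. On the raw scale a doubling lies 1.0 from no change and a halving only 0.5, so decreases count for less in averages and in clustering. Raw ratios are also right-skewed, so their mean depends on the spread as well as the typical change, and a t-test on them is less efficient.

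Two things are at stake. The reported average fold changes would lean upward, and real differences between the two progression points would be missed more often. Decreases matter here: PTEN loss is central to the rationale in Section 2.3, and PTEN is among the RPPA proteins of interest in Section 9.2.1.2. Tissue is also scarce, because Section 9.1 makes the second progression biopsy optional.

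**Working it through.** **Inputs**

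- SD of the log2 change: 0.95, from the kinome plan. No RPPA figure exists, so this is an assumption; range 0.5 to about 1.3.
- Patients per interval: not stated for RPPA. I assume 9 (the number of kinome pairs) to 20, with 37 evaluable patients as the ceiling.
- Two-sided alpha 0.05, as in the kinome plan.
- Log-normal ratios, a single protein, one value per patient.

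**Step 1: the plan's own figure.** RPPA has no power statement, so the nearest is Table 5: 8.93, 81.69, 97.39 and 99.61% for log2 differences of 1.00, 1.58, 2.00 and 2.32 with 9 pairs. A paired t-test with SD 0.95 reproduces all four values when the per-test alpha is set for a 5% false discovery rate with 10 of 100 kinases changed:

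alpha = power × 10 × 0.05 / (90 × 0.95); for the second value, 0.8169 × 0.5 / 85.5 = 0.00478.

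So 0.95 acts as the SD of a paired log2 change, which is the quantity a log2 RPPA ratio would be.

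**Step 2: mean raw ratio with no true change.** E[ratio] = exp((SD × ln 2)² / 2).

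- SD 0.5: exp(0.3466²/2) = 1.06
- SD 0.95: exp(0.6585²/2) = 1.24
- SD 1.3: exp(0.9011²/2) = 1.50

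Subtracting the median does not remove this. At SD 0.95 the mean of the centered raw ratios is still +0.21 (n = 9) to +0.23 (n = 20). On log2 the mean is 0.

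**Step 3: the planned comparison with equal spread and no change.** The upward shift is the same at both intervals and cancels. Simulated error of the raw two-sample test is about 4 to 5%.

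**Step 4: power for a true 2-fold difference between intervals (simulation).**

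| Setting | Log2 SD | Raw | Log2 |
|---|---|---|---|
| Two-sample, 9/9 | 0.5 | 97% | 98% |
| Two-sample, 9/9 | 0.95 | 46% | 56% |
| Two-sample, 20/20 | 0.95 | 83% | 90% |
| Two-sample, 9/9 | 1.34 | 21% | 32% |
| Two-sample, 20/20 | 1.34 | 47% | 63% |
| Paired, independent changes, n = 12 | 0.95 | 55% | 65% |
| Paired, independent changes, n = 20 | 0.95 | 81% | 88% |
| Paired, correlation 0.5, n = 12 | 0.95 | 80% | 91% |
| Paired, correlation 0.5, n = 20 | 0.95 | 96% | 99% |

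The correlated rows matter because both ratios for a patient share the pre-treatment sample; 0.5 is an assumed value. At SD 0.95 the smallest gap is 99 - 96 = 3 points. The largest, about 15, is for 9 pairs with correlation 0.5. There the SD of the difference is 0.95 × √(2 × 0.5) = 0.95, so log2 power is 79%. Over n = 9 to 20, paired or not, the loss is at most about 2 points at SD 0.5 and about 11 to 23 at SD 1.3.

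**Step 5: unequal spread, no true change.** Take SD 0.7 at one interval and 1.2 at the other (assumed). The raw means are exp(0.4852²/2) = 1.12 and exp(0.8318²/2) = 1.41, a difference of 0.29. Error is 8% raw against 5% log2 at 20/20. At 37/20, with the wider spread in the smaller group, it is 19% against 9%. The remaining 9% comes from Student's equal-variance test with unequal numbers, not from the scale.

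**Step 6: pooling.** With 10 proteins per cluster and a within-patient correlation of 0.3 (both assumed), treating all ratios in a cluster as independent gives a null error of about 28% raw and 31% log2. The log step does not help there.

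**The case against.** - **Raw analysis is inferred from silence.** The plan names ratios and omits a log step; it does not say that logging is ruled out. If the values are logged before use, the problem disappears. This stands as a limit. Even so, an analyst following the text would average ratios, and the kinome paragraph shows that the scale could have been stated.
- **The upward shift does not reach the planned test.** This also stands. A reader might infer that the t-test will declare false increases. Against a ratio of 1 at SD 0.95 it would, with null error of 5, 12 and 30% at n = 9, 20 and 37. The plan contains no such test; it compares intervals, where the shift cancels under equal spread.
- **The size is uncertain.** The SD comes from another assay, and neither the number of patients nor the pairing is given. At SD 0.5 the effect is close to nil. Hence a range and not one figure.
- **Little depends on it.** A reader might infer that these tests choose the resistance candidates. Sections 9.2.2 and 13.4 build that catalogue from sequencing. Section 9.2.1.1 takes further IHC proteins from the RPPA assay, without tying them to this t-test. No decision rule or sample size uses it.
- **Pooling within clusters is the larger fault in the same sentence.** On the assumed figures in Step 6 this is right, so a log step alone does not make the test valid.

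**Conclusion.** The point holds as a minor one. On the text as written, RPPA changes are summarized on a scale that overstates average increases by about 6, 24 or 50% when nothing has changed, at log2 SDs of 0.5, 0.95 and 1.3, and that gives decreases too little weight. For the planned between-interval test the main cost is power, from almost nothing at SD 0.5 to roughly 11 to 23 points at SD 1.3. Inflated false-positive error from the scale requires the spread to differ between intervals.

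These sizes rest on log-normal ratios, a borrowed SD, assumed patient numbers, and one protein with one value per patient. They are not the power of the cluster-pooled test in the plan, which cannot be computed from what is stated. The primary endpoint and both two-stage decisions are unaffected.

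**What to change.** In the RPPA paragraph of Section 13.4, state that progression/pre-treatment ratios are log2-transformed before median-centering, clustering and testing, and that results are reported as geometric mean fold changes, in line with the kinome analysis. This needs one clause and no extra samples, assays or patients.

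A second sentence should deal with pooling: average the log2 ratios within each cluster for each patient, and run the t-test on one value per patient per interval. That also costs no data.
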